### C12b. Depressed Adult Clients

**Recruitment.** Adult clients ( $N=625$ ; target  $N=500$ ) seeking treatment for depression at Centerstone will be eligible for enrollment in the research study. As this is a pragmatic trial (Thorpe et al., 2009) client participation criteria include: (a) age 18 and above; (b) depression is one of the primary treatment foci based on diagnosis made by clinicians using usual care interview methods to reflect major depressive disorder, dysthymic disorder, depressive disorder NOS, adjustment disorder with depressed mood; (c) significant depressive symptom severity (PHQ-9 total score  $> 9$ ); (d) receipt of individual psychotherapy; (e) fluency in English; and, (f) new client beginning treatment (g) with an enrolled study clinician during the proposed funding period. Exclusion criterion is minimal: an inability to sign the consent due to lack of competence or inability to read. Intake clinicians will be trained to identify eligible clients and assess if they would be interested in hearing more information about a research study. If the client agrees, the clinician will share the client's contact information with the project coordinator. Because Centerstone has a strong research commitment, clinicians and clients are accustomed to a research environment where the option to participate in studies is more routine than in many community mental health centers. Both Centerstone clinicians and clients have participated in a number of research studies and recruitment is expected to be very straightforward. However, to supplement this approach, Co-I ([name], Director of Centerstone Research Institute) will run weekly queries of the Centerstone database (in accordance with Health and Human Services guidance) to identify eligible clients (see Human Subjects for previously used HIPAA compliant procedures) who will be contacted by our project coordinator to assess interest in study participation. Once a client has been enrolled, the study team will flag the client in the electronic health record to initiate study procedures for the clinician. Given the number of clients seeking treatment for depression at Centerstone ( $> 30,000/yr$ ), we anticipate that our client recruitment goal will be feasible.

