**Data Collection.** The goal of client data collection is to determine if routine measurement (in the standardized condition) improves depressive symptom severity and whether adaptations to the MBC assessment schedule (tailored condition) have differential effects on depression outcomes. Clients will complete the PHQ-9 on a tablet kiosk in the waiting room according to site-generated guidelines; this information will be automatically fed into the electronic health record for clinicians to review in session. Given the potential for variable PHQ-9 completion in the tailored condition (based on the site-generated guideline), we will also have clients enrolled in both conditions complete the PHQ-9 at baseline (immediately post consent) and at week 12 of treatment (via automated phone survey). The 12-week window

reflects a commonly used time period in randomized clinical trials during which depressive symptoms are expected to remit. We will also supplement data collection with client 5-axis diagnoses and employment status captured in intake and progress review reports.

**Retention.** At recruitment, clients will complete a consent form and provide options for multiple contact methods (e.g. multiple phone numbers, address). Centerstone has consistently achieved greater than 75% client retention in federally-funded randomized trials (CATIE, Keefe et al., 2007; STAR\*D, Insel, 2006). We will replicate previous efforts to maximize retention in the proposed study. In order to have sufficient power to detect statistical significance and account for client attrition, we intend to recruit 1.25 more client participants ( $N=625$ ) to assure that we achieve our enrollment goal ( $N=500$ ).

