**Aim 1: Hypotheses:** Tailored implementation will outperform standardized in terms of (H1a) fidelity. MBC clinician fidelity was evaluated with two variables: (1) whether the PHQ-9 was recorded in the EHR, and (2) among encounters for which the PHQ-9 was recorded, whether it was discussed. Both outcomes were modeled using generalized linear mixed models with a logit link function for a binary distribution using the lme4 package. All models included random intercepts for clinicians and patients. Models for both outcomes were constructed in an identical sequence. Models comparisons in the model-building sequence described below were evaluated using the Bayesian Information Criterion (BIC); the model with the better BIC was selected for presentation. Several unconditional growth models (i.e., models with only parameters for time) were fit (i.e., linear, quadratic, log-transformed number of months). After establishing the unconditional growth model, additional fixed effects were added in the following sequence: (1) group main effect and (2) group x time interaction. Finally, new versus existing patient status was investigated as a main effect using a dummy variable for new patient status and as a patient status x group interaction.

**Aim 2: Hypotheses:** Contextual mediators will be leveraged in the tailored condition, but serve as barriers in the standardized condition. Mediation models were fit to evaluate which contextual factors (based on clinician-completed surveys, Table 5; and, clinician selection of drop-down menu reasons for MBC deviations captured in the electronic health record) mediate the impact of the implementation condition on both clinician- and client-level outcomes. The two critical effects underlying mediation were evaluated in separate models: treatment condition predicts the mediator (path *a*) and the mediator predicts the outcome (path *b*). Specifically, mediators were assessed at the conclusion of the implementation window and the mediators were used to predict PHQ9 completion in the sustainment window. The *a* path was assessed using linear mixed models with Satterthwaite degrees of freedom

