### **Clients**

**Inclusion Criteria.** As this is a pragmatic trial (Thorpe et al., 2009), clients will be eligible for the study if they: 1) are age 18 and above; 2) have depression as one of the primary treatment foci: diagnosis will be made by clinicians using usual care interview methods and can include any of depressive disorder diagnosis (e.g., major depressive episode, dysthymic disorder); 3) have significant depressive symptom severity (PHQ-9 total score > 9 at intake); 4) will receive individual psychotherapy; 5) are receiving psychotherapy treatment with an enrolled clinician during the proposed funding period.

**Exclusion Criteria.** Because of the pragmatic nature of this trial, there is only one exclusion criterion for clients. Specifically, clients will be excluded if they are unable to provide verbal consent due to severe mental illness or inability to read, for instance.

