Welcome Packet, which will, contain the informed consent, authorization for the release of health information for research, and a stamped and return-addressed envelope will be sent to the client's address. The client will a \$5 gift card as compensation for PHQ-9 completion in the initial phone screen. If the client signs and returns the release of health information either via the pre-paid envelope or in person at their next session (additional information on the informed consent process can be found below in Section XII: Informed Consent Process), s/he is enrolled in the study. At this point the client will receive an additional \$5 compensation. If the client consents to research participation and the authorization for the release of health information for research, their verbal PHQ-9 and demographics data from the initial phone screen will be utilized as a baseline measure and be transported to IU for storage, given that the consent includes that the PHQ-9 completed for the eligibility screener and demographics questions can be used for the purposes of research. The 5-Axis diagnosis and employment, status, program activity involvement (i.e., type, start date, end date, care coordinator involved, face-to-face contact, location, reasons for discharge), date of first and last service, date of intake session, admission status (active/inactive), body mass index (BMI), age at BMI, demographics, medication use (i.e. prescription type, dosage, units, number of pills), and blood pressure (Appendix C.3) will also be retrieved from the clinician's intake report and health records to obtain information about comorbidities and functioning for all enrolled clients. This information will be retrieved by a trained Centerstone Research employee who will de-identify the information and then provide it to the research team.

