## **Phase 2 (Months 8-38)**

*Client's Treatment (weeks 0-11).* Clients in the standardized condition will be asked to complete the hard copy PHQ-9 forms in the waiting room prior to every session with their enrolled study clinician, while clients in the tailored condition will complete the PHQ-9 according to the measurement-based care guidelines defined by the implementation team at each site. In all cases, clients will fill out the hard copy PHQ-9 prior to a session located in waiting room kiosks and completing the survey should only take about five to ten minutes. The client will then hand the completed PHQ-9 to his or her clinicians who will then enter it into the electronic health record so that the clinicians can review the PHQ-9 scores with the clients during the session. The CRI RA will pull the PHQ-9 data for all enrolled clients across the course of their treatment and provide it to the research team using the 9-digit anonymous identification number. In addition to the PHQ-9, clients will be asked to respond to a telephone or text message-based survey after each psychotherapy session to inquire as to whether their clinician discussed PHQ-9 scores in the session immediately preceding (Yes/No/NA) (Appendix C.4). Client can earn \$2 for every survey they complete for up to \$20. So clients may be able to earn an additional \$20 for completing these surveys after each session and the amount attained will be mailed with the \$10 incentive for completing the week 12 PHQ-9 (described below).

*Client's Treatment (week 12).* Clients will be reassessed for depression symptom severity via a phone interview (like the initial screen) at week 12 of their treatment, regardless of number of treatment sessions attended (Appendix C.2). A postcard reminder may be sent to clients before the phone interview as a reminder. The project coordinator and CRI RAs will track client time since entering treatment, beginning with the intake assessment. Clients will be mailed \$20 as an incentive for completing the week 12 assessment.

*Client's Treatment (week 13 and beyond).* Upon completion of the telephone assessment at week 12, PHQ-9 data collection for all enrolled clients will continue to occur according to the site guidelines for the duration of the study funding-period.

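### As worded, the week-12 PHQ-9 is timed from entry into treatment but the baseline PHQ-9 from enrolment, so existing clients would have 12 weeks minus their time already in treatment; the sections need reconciling

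*Combined protocol and SAP*

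**What the plan says.** **Follow-up clock.** Section VII (Clients, Phase 2, week 12) places the follow-up phone PHQ-9 "at week 12 of their treatment, regardless of number of treatment sessions attended". Study staff "will track client time since entering treatment, beginning with the intake assessment".

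**Baseline.** Section VII (Clients, Phase 1) says that the PHQ-9 "from the initial phone screen will be utilized as a baseline measure" once the client has consented and authorised release of records. C12b (Data Collection) likewise has clients in both arms "complete the PHQ-9 at baseline (immediately post consent) and at week 12 of treatment (via automated phone survey").

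**Who is enrolled.** C12b (Recruitment) requires a "new client beginning treatment". The client criteria in Section V.B have no such requirement and admit clients who "are receiving psychotherapy treatment with an enrolled clinician during the proposed funding period".

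**Analysis.** Under Aim 1, C13a states that "new versus existing patient status was investigated" in the fidelity models. The only depression model it describes, under Aim 3, compares intake with week 12. It includes patient status as a covariate, then adds implementation group and session counts, and also examines interactions with new-patient status. It lists no term for the time between the two PHQ-9 scores.

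**Related timing.** Section V.C closes client recruitment at month 35 so that the 12-week assessment can be finished by the end of Phase 2 at month 38. The payment justification in Section XI uses *intake* for the phone PHQ-9.

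**The concern.** The change score starts at one event (enrolment) and ends at a date counted from another (entry into treatment). If only new clients are enrolled, the two events nearly coincide and little is lost. If clients already in treatment are enrolled, each has a different and shorter follow-up.

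This would matter in three ways.

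- Client depression severity is the client half of the co-primary aim (H1b). C12b justifies 12 weeks as the period over which symptoms are expected to remit, and a shorter interval does not match that rationale.
- Mixing short and full intervals would tend to dilute a change that builds up over time.
- Sites are randomised before Phase 2 and clients are recruited during it. The mix of new and existing clients could therefore differ between arms, and follow-up length would then differ with it.

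**Working it through.** **Step 1: the plan's own figure.** Section V.C allows 38 − 35 = 3 months for the last client's 12-week assessment. In weeks this is 3 × 365.25 / 12 / 7 = 13.04. The cut-off therefore works for a 12-week clock that starts at recruitment.

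**Step 2: the interval on the Section VII wording.** Let t be the weeks from treatment intake to the phone-screen PHQ-9. Follow-up falls 12 weeks after intake and baseline falls t weeks after intake, so

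interval = 12 − t.

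**Step 3: new clients.** Section XII describes daily record queries, a call within 24 hours of identification, and a mean of 13 days from intake to the first session.

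| Phone screen after intake | Interval (weeks) | Shortfall (weeks) |
|---|---|---|
| 1 day | 12 − 1/7 = 11.86 | 0.14 |
| 2 days | 12 − 2/7 = 11.71 | 0.29 |
| 13 days (just before an average first session) | 12 − 13/7 = 10.14 | 1.86 |

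**Step 4: existing clients.** The documents do not give t, so the values below are assumptions that show the range.

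| t assumed (weeks) | Interval (weeks) |
|---|---|
| 2 | 10 |
| 4 | 8 |
| 8 | 4 |
| 12 | 0 |
| 16 | −4 |
| 26 | −14 |

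A zero or negative value means that the scheduled date falls on or before baseline. No such call can serve as a follow-up, and the plan does not say what would be done instead.

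**Step 5: what the model can absorb.** A patient-status term, with its interactions, allows new and existing clients to differ on average. It takes one value for all existing clients, whereas 12 − t varies from one to the next. It therefore cannot adjust for the spread of intervals within that group.

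**Step 6: the interval after the fix.** Counting week 12 from the baseline PHQ-9 gives 12 weeks for every client, and 12 is less than the 13.04 weeks available after month 35.

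**The case against.** The strongest reply is that *intake* may simply mean the enrolment PHQ-9. Section XI uses the word that way, Section V.B attaches it to the PHQ-9 threshold that the phone screen tests, and the Aim 3 model measures change from intake although the phone screen is the baseline. The month-35 cut-off also presupposes a clock from recruitment. On that reading every client has 12 weeks. This stands as a real ambiguity. It does not remove the point, because Section VII refers to time since entering treatment, and Section XII uses *intake* for the clinic event that precedes the first session.

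The second reply is that the recruitment procedure in Section XII reaches clients close to intake, before their first session, where the shortfall is under 2 weeks. That is right for new clients. It does not account for the existing patients whom C13a analyses, and no section defines them or says how their week-12 call was timed.

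The third reply is that C13a examines interactions with patient status. If implementation group is among the variables interacted, the new-client contrast can already be separated. That also stands, but the varying intervals among existing clients remain unadjusted.

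**Conclusion.** The concern holds as a conflict between sections with a definite arithmetical consequence. On the Section VII wording, existing clients have 12 − t weeks of follow-up and no valid week-12 point once t reaches 12. New clients lose about 0.1 to 1.9 weeks. This rests on reading *intake* as entry into treatment and on existing clients being enrolled, which Section V.B and C13a support and C12b contradicts.

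Three stronger readings are tempting, and the documents support none of them.

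- A reader might infer that existing clients were in fact followed for less than 12 weeks. The documents do not say how their calls were timed. The 22.8% without a 12-week interview is not split by patient status.
- A reader might infer that the comparison of arms is biased. That would need the mix of clients or their time in treatment to differ by arm, and neither is reported. It is a possibility created by recruiting after site allocation, not a finding.
- A reader might put a figure on the loss. With a share s of existing clients and t uniform over 0 to 12 weeks, the mean interval is (1 − s) × 12 + s × 6, or 11.4, 10.5 and 9.0 weeks for s = 10%, 25% and 50%. Both inputs are assumed, and the calculation leaves out anyone beyond 12 weeks. It is an illustration only; the actual size is unknown.

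**What to change.** 1. State in Section VII and C12b that week 12 is counted from the baseline (enrolment) PHQ-9 for every client, and use *intake* for one event only. Reconcile C12b and Section V.B on whether existing clients are eligible, and bring Section V.C, Section VII and Section XI into line on the clock. This costs wording and a scheduling date, with no extra client contact.
2. C13a is written in the past tense and reports 12-week missingness, so rescheduling may come too late for many clients. For those already assessed, derive weeks from baseline to follow-up from the dates of the two PHQ-9 calls, which the trial should hold. Report the distribution by arm and patient status. The intake-session date, which Section VII already retrieves, gives time in treatment at baseline.
3. Use actual elapsed weeks in the Aim 3 depression model.
4. Report the implementation-group contrast in new clients alone as a sensitivity analysis.

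The cost of items 2 to 4 is a small amount of extra analysis, and lower precision in the new-client subset.

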## **Administrators: Across Both Conditions (i.e., Standardized and Tailored)**

### **Phase 2 (Months 8 – 38)**

*5-Month Active Implementation.* Administrator from each site will be asked to participate in a 30 minute individual interview either in-person or phone-based at the beginning of Phase 2 (Appendix E.2 and E.3). Administrators who participate in the individual interview will receive \$20 compensation. Individual interviews will be recorded and transcribed using VoiceBase technologies with data de-identified for the purposes of qualitative coding.

In addition, one administrator per site will be invited to participate on the implementation team at each site. The implementation team consists of research team members, site administrator, 2-4 clinician opinion leader and champion, a client, and office professional. This team will convene for triweekly meetings during the 5-month active implementation phase and they are encouraged to meet without the researchers present during the 10-month follow-up period to facilitate identification of additional barriers (the number of actual meetings and attendance will be documented). Administrators will be informed that the meetings will be audio-recorded for research team coding purposes, with the focus on capturing the barriers that emerged and the function of the discussions. Administrators will be reminded at the beginning of each session not to use client names during consultation sessions to protect client confidentiality. Audio-recorded sessions will be transcribed using the procedures outlined for the focus groups. No administrator study participant identifying information will be retained in the transcripts and only 6-digit anonymous identification numbers will be used. The form found in Appendix B (MBC Barriers Coding Form; Appendix B.1) will be completed by implementation teams during their

triweekly meetings; deidentified MBC Barriers Coding Forms will be analyzed for the purposes of research. Additionally administrators will complete the battery of self-report measures (the same one that clinicians complete) and receive \$50 compensation at the baseline, 5-month follow up, and 10-months after the active implementation period. Finally, a battery of surveys will be administered in-person and completed by those on the implementation teams at 5-months and 15-months during an implementation team meeting. These surveys include the Acceptability, Feasibility, Appropriateness for Implementation Teams and Conditions (Lyon, 2011; Appendix A.16-1, A.16-2); [name] Implementation Team Survey (A.19), and Edmondson Team Measure (Edmondson et al, 1999; A.20). These surveys will take about 25 minutes to complete and staff on the implementation team will receive \$15 in compensation per assessment point.

At the end of the active implementation period, the administrator will be invited to participate in the Contamination interview. This interview will be conducted in person or on the phone and will take about 30 minutes to complete.

### **Office Professionals: Across Both Conditions (i.e., Standardized and Tailored)**

#### **Phase 2 (Months 8 – 38)**

*5-Month Active Implementation.* One office professional per site will be invited to participate on the implementation team at each site. The implementation team consists research team members, site administrator, 2-4 clinician opinion leaders and champions, a client, and office professional. This team will convene for triweekly meetings during the 5-month active implementation phase and they are encouraged to meet without the researchers present during the 10-month follow-up period to facilitate identification of additional barriers (the number of actual meetings and attendance will be documented). Office professionals will be informed that the consultation and training sessions will be audio-recorded for research team coding purposes, with the focus on capturing the barriers that emerged and the function of the discussions. Office professionals will be reminded at the beginning of each session not to use client names during consultation sessions to protect client confidentiality. Audio-recorded sessions will be transcribed using the procedures outlined for the focus groups. No office professional study participant identifying information will be retained in the transcripts and only 6-digit anonymous identification numbers will be used. The form found in Appendix B (MBC Barriers Coding Form; Appendix B.1) will be completed by implementation teams during their triweekly meetings; deidentified MBC Barriers Coding Forms will be analyzed for the purposes of research. Finally, a battery of surveys will be administered in-person and completed by those on the implementation teams at 5-months and 15-months during an implementation team meeting. These surveys include the Acceptability, Feasibility, Appropriateness for Implementation Teams and Conditions (Lyon, 2011; Appendix A.16-1, A.16-2); [name] Implementation Team Survey (A.19), and Edmondson Team Measure (Edmondson et al, 1999; A.20). These surveys will take about 25 minutes to complete and staff on the implementation team will receive \$15 in compensation per assessment point. Additionally, all office professionals will be invited to participate in the study by completing parts of the abbreviated baseline battery that are applicable to their position at the baseline. The battery will take about 30 minutes to complete and office professionals will be compensated \$20 for completing the battery at each of the three assessment point. They will complete the battery at the same time points as clinicians: at baseline, at the 5-month follow up and 10 months following the active implementation period.
